### 7.2 Pregnancy Test

Women of childbearing potential (women who are not surgically sterile or postmenopausal defined as amenorrhea for >12 months) must perform a pregnancy test (urine based) during screening. The test result must be documented in the source data.

During the study it is recommended to use highly effective contraceptive method (failure rate less than 1% per year) such as injectable, combined oral contraceptives or hormonal intrauterine devices (IUDs).

### 7.3 Demographics

Subject demographics, including age, gender, and race/ethnicity, will be documented at the screening visit.

### 7.4 Medical History & Dental History

Percentage of total surfaces with plaque

The dental history & medical history has to be obtained at the screening visit. It should include dental status information including extraction socket position according to FDI and description of opposing and adjacent dentition.

Oral hygiene assessment could be performed according to the standard of care at the site (although it is not mandatory, it is recommended to use the Full Mouth Plaque Index (PI) according to O'Leary et al. 1972 and the Full Mouth Bleeding on Probing (BoP) Index according to Ainamo and Bay 1975.).

Full mouth PI (O'Leary et al. 1972) should be measured on each single tooth mesial, distal, facial and lingual with the following formula:

No. of surfaces with plaque x 100

Total no. of surfaces

Version 6.0

Full mouth BoP (Ainamo and Bay 1975) should be measured on each single tooth mesial, distal, facial and lingual with the following formula:

Percentage of total surfaces bleeding = No. of surfaces bleeding x 100

Total no. of surfaces

Current diseases will be evaluated by the investigator based on the information available (letter from general physician or oral communication with the subject).

#### 7.5 Inclusion / Exclusion Criteria

See 5.1. and 5.2

#### 7.6 Cone Beam CT

In order to perform radiographic measurements of the residual bone height a cone beam computed topography (CBCT) not older than 12 months should be available. Dental cone beam CT scan (CBCT) technique provides a 3-dimensional view of the area of interest and therefore offers sufficient information on sinus anatomy to plan for sinus floor elevation.

**7.7 Adverse Events** (please see section 9. Definitions of Adverse Events and Device deficiencies (from ISO 14155))

Any adverse event must be documented at each study visit until the end of the study.

#### 7.8 Concomitant Medications

Any concomitant medication as well as changes in the concomitant medication, procedures, or supportive therapies must be documented at each study visit (except vist 1) until the end of the study.

#### 7.9 Randomization

Subjects will be randomized either to the test group receiving Straumann® VivOss™ or comparator group receiving Geistlich Bio-Oss®. The master randomization list will be kept in a secure repository in the office of the Sponsor. The study centers have to contact the Sponsor by email or phone to request randomization of a subject, the Sponsor will send a randomization form including randomization details via email or fax. Although this study is not blinded, no access to the randomization list will be available to the study centre, the external Monitors, the subjects and the Straumann non-Clinical-Research project team.

Site/s of Biopsy

The site of biopsy in each sinus depends on the number of implants to be placed in the sinus. If more than one implant will be placed the most preferred site will be position 6, followed by position 5, followed by position 7, the least preferred position is position 4.

Version 6.0 Page 20 of 47

If more than one implant is placed, the investigator should take 2 biopsies following the preference list above. The second biopsy should be taken as backup in case the first biopsy cannot be evaluated.

**Bilateral Sinus Floor Augmentation** 

If a patient needs augmentation in both sinus, one sinus is randomised as study sinus. If the sinus is randomized into test group and receives Straumann® VivOss™, the opposite sinus should be augmented with Geistlich Bio-Oss® and vice versa. In bilateral patients biopsies should be taken from both sinus according to the instructions above.

### 7.10 Augmentation

The Sponsor recommends to follow the lateral window technique as described in the ITI Treatment Guide Volume 5 (2011). A collagen membrane *Geistlich Bio-Oss®* should be used to stabilize the bone window, this membrane should cover the complete window and should not consist of several pieces. Afterwards the gingiva should close the wound completely and should be sutured without any tension.

### 7.11 Secondary Inclusion criteria

See 5.3.

### 7.12 Intra-oral Photographs

Digital intra-oral photographs in raw-format should be taken at each study visit to document the procedures:

Visit 2: At surgery visit the investigator should take the following lateral pictures:

- before surgery
- before removing the window
- open sinus
- filled sinus
- window back in place
- membrane placed on window
- after suture

Visit 3: Lateral pictures:

- wound before suture removal
- wound after suture removal

Visit 4: vertical pictures:

- open flap
- after biopsy
- before implant placement
- implant placed flap open
- after suture

Visit 5: vertical pictures

- wound before suture removal
- wound after suture removal

Visit 6: vertical pictures

- before loading
- after loading

Version 6.0 Page 21 of 47

Photographs should be labelled as below for easy identification of the subject:

Study CR 03/13: 0313 Visit number: \_V1 Patient No.: \_01 25

e.g. 0313\_V1\_0125 0313 V3 0205

#### 7.13 Suture removal

Sutures should be removed according to the standard of care at the clinic.

### 7.14 Biopsy

The bone biopsies are retrieved in both the test and the comparator group.

The bone biopsies will be retrieved from the central part of the dental implant osteotomy and will be processed together with the trephine burr. The biopsies will be immersed and fixed in buffered formalin. Further processing of the biopsy and evaluation of the histologies is described in detail in a separate technical procedure protocol. The biopsy-samples will be labelled with:

- Patient number
- Position (FDI)

# 7.15 All biopsy-samples will be analysed centrally in Zürich, Switzerland. Implant placement

After the biopsy the study center should follow their standard of care regarding implant bed preparation and implant placement. The details of the used implant have to be documented.

#### 7.16 Wound healing assessment

Wound healing details have to be documented.

### 7.17 Periapical x-rays

A periapical x-ray has to be taken to document the success of the implant in regards to radiolucency.

#### 7.18 Implant survival

Implant survival has to be documented

### 7.19 Implant success

An implant will be deemed a success if all of the following success criteria (according to Buser et al 1992) apply:

- Absence of persisting subjective discomfort such as pain, foreign body perception and or dysaesthesia (painful sensation)
- Absence of a recurrent peri-implant infection with suppuration (where an infection is termed recurrent if it is observed at two or more follow-up visits after treatment with systemic antibiotics)
- Absence of implant mobility on manual palpation

Version 6.0 Page 22 of 47

Absence of any continuous peri-implant radiolucency

### 8 Study conduct

#### 8.1 Visit Windows

The goal should always be to keep the given time point of each visit. However the time windows given below are the limits to be kept to perform according to the protocol.

Visit 0	Visit 1	Visit 2	Visit 3	Visit 4	Visit 5	Visit 6
Informed Consent	Screening Visit	Sinus elevation (Baseline)	Wound healing assessment	Implant placement	Wound healing assessment	Initial implant loading
28-2 days before screening	14-0 days before Baseline	Day 0	Day 7-14	6 months ± 7 days	2 weeks after visit 4	4 months ± 1 month after visit 4

### 8.2 Screening Failures

Any subject that has signed the informed consent form, is not randomized and does not receive the study device is considered a screening failure. In the event of a screening failure, the case report forms should be completed up to the visit when the subject was determined to be a screening failure. The "study termination form" should also be completed and a new subject should be recruited if the recruitment period is ongoing.

In case of a screening failure according to an eligibility criterion that may be re-evaluated at a later time point (e.g. oral hygiene), a re-screening of the patient is possible as judged by the investigator if the recruitment period is ongoing. In this case, a "re-screening form" should be completed instead of the "study termination form".

#### 8.3 Subject Completion / Withdrawal

It is possible that a subject may withdraw from the study at any time without prejudice and will be offered an alternative treatment for his/her dental condition. Subjects will be advised of the need for the prescribed follow-up visits for their ongoing care, well-being, and collection of relevant study data. All subjects must agree to return to the clinic to complete these follow-up visits.

The investigator may withdraw any subject from the study in the case of:

- non-compliance with the protocol
- a serious adverse event or an adverse event, in the opinion of the investigator, which prevents the subject's further participation in the study.

If a subject is withdrawn from the study as outlined above, the subject must be followed for reporting of adverse events. Withdrawn subjects will be followed according to the standard of care at the study centre.

Version 6.0 Page 23 of 47

### 8.4 Subject Replacement Policy

For any subject who for any reason drops out of the per-protocol population a new subject with a new number should be allocated if the recruitment period is ongoing.

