### 4.4 Number of Subjects

This study will be performed in two clinical centres, one in Germany and one in Switzerland; these centres are expected to recruit 50 subjects in total, 25 subjects in test group, 25 subjects in control. Planned subject recruitment period is 3 months. The recruitment is competitive. Recruitment will be stopped as soon as recruitment is complete.

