### 5.4 Treatment Groups

In total 50 subjects will be randomize equally into test or control group (25 patients in each group).

The subjects in the test group receive sinus floor elevation with HA/TCP 10:90 (*Straumann*® *VivOss*™) via a lateral approach. In the comparator group, subjects receive sinus floor elevation with demineralized bovine mineral (Bio-Oss®) via a lateral approach.

Both groups follow the same schedule of assessments.

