### 10.2 Statistical Hypotheses

The primary endpoint of this study is the histological evaluation of the ratio of newly formed bone to residual bone graft in *Straumann*® *VivOss*™ compared to *Geistlich Bio-Oss*® at visit 4 (6 month ± 7 days, after sinus elevation).

In this study the following hypothesis will be tested

Straumann® VivOss™ combined with Bio-Gide shows a significantly higher ratio of newly formed bone to residual bone graft compared to Geistlich Bio-Oss® combined with GeistlichBio-Gide at visit 4 (6 month ± 7 days, after sinus elevation).

- T: Test Group
- C: Comparator Group

Testing for Superiority (based on the per protocol (PP) data set):

 $H_{0S}$ : T = C

 $H_{1S}$ :  $T \neq C$ 

 $H_{0S}$  is the null hypothesis, claiming that there is no difference in the true mean of ratio of newly formed bone to residual bone graft after 6 months between the test group and the negative control group

H1S is the alternative hypothesis claiming that the true mean change of ratio of newly formed bone to residual bone graft after 6 months is unequal in the two treatment groups; either higher or lower in the test group than in the negative control group.

- T is the true mean at 6 months of the ratio of newly formed bone to residual bone graft in the test group.
- C is the true mean at 6 months of the ratio of newly formed bone to residual bone graft in the control group.

The secondary efficacy variables in this clinical study are:

- Survival rate of study implants evaluated at visit 6 (initial implant loading)
- Success rate of study implants evaluated at visit 6 (initial implant loading)

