### 10.4 Populations for Analysis

### 10.4.1 Per Protocol Set (PP)

Randomized subjects who terminated the study and in whom no major protocol violations have been observed.

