### 10.4.2 Full Analysis Set (FA)

This data set will include all randomized subjects who have received at least one study device and from whom at least one measurement of post randomization data is available. It will include subjects even with major protocol violations and premature termination. The FA Set includes the PP Set.

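### The superiority test is run on the per-protocol set, so randomised and treated subjects lost after randomisation leave the primary comparison, and section 8.4 refills their places so that the loss does not show

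*Combined protocol and SAP*

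**What the plan says.** Section 8.4 provides that "For any subject who for any reason drops out of the per-protocol population a new subject with a new number should be allocated", with the condition "if the recruitment period is ongoing". The rule reaches randomised subjects. Section 10.4.1 defines PP as "Randomized subjects who terminated the study and in whom no major protocol violations have been observed", and subjects who fail before randomisation have their own rule in section 8.2.

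Section 10.2 introduces the primary hypothesis with "Testing for Superiority (based on the per protocol (PP) data set". The FA set of section 10.4.2 is wider: "It will include subjects even with major protocol violations and premature termination". No primary or sensitivity test is assigned to it.

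Section 8.3 lets the investigator withdraw a subject for non-compliance, or for "a serious adverse event or an adverse event, in the opinion of the investigator", that prevents further participation. The trial is open label (section 4.1).

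On numbers, section 5.4 says "In total 50 subjects will be randomize equally into test or control group", 25 in each. Section 10.3 derives the 25 with no allowance for loss. Section 4.4 says "Planned subject recruitment period is 3 months", and section 4.5 places the primary endpoint at 6 months ± 7 days after sinus elevation.

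**The concern.** Randomisation makes the arms comparable at the moment of allocation. PP membership is settled later, by events that the graft can cause and by an investigator who knows the treatment. If such events are more common in one arm and go with a different ratio of new bone to residual graft, the PP difference is no longer a fair estimate of the treatment effect.

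Section 8.4 adds a reporting problem. Once losses are topped up, a primary analysis of 25 against 25 looks complete although more than 50 subjects may have been randomised. Nothing in sections 8.4 or 10 asks for the numbers lost and added by arm, and section 8.4 does not say how the new subject is allocated.

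The primary claim of superiority is at stake, because it is tested only on this set.

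**Working it through.** **1. The plan's own figure.** Inputs from section 10.3: difference 0.4, SD 0.5, two-sided 5%, power 80%. With the normal formula,

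n = 2 × (1.960 + 0.842)² × (0.5/0.4)² = 24.5, rounded up to 25 per group.

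This matches the plan, and all seven entries of Table 1 reproduce in the same way. The exact t-test needs 26. The 25 is therefore a number of evaluable subjects with no margin, and section 8.4 is the only provision for losses.

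**2. Which losses can be replaced.** Recruitment is planned for 3 months and the biopsy is at 6 months, so on the planned timetable a replacement can only follow a loss that occurs before that subject's biopsy. Assume uniform entry over 3 months and loss uniform over the 6 months to biopsy. The share of losses that fall while recruitment is open is then (3 × 3 / 2) / (3 × 6) = 4.5/18 = 25%. Later losses are not replaced, but they still leave PP.

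**3. Bias from excluding failures.** Assumptions: no true difference over all randomised subjects; SD 0.5; a fraction f of the test arm fails, with a mean ratio lower by g than the rest of that arm; no failures in control. For the whole test arm to have the control mean, the non-failures must lie f × g above it. PP keeps only the non-failures, so

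bias = f × g.

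For 2 of 25, f = 0.08 and g = 0.5: bias = 0.08 × 0.5 = +0.04. For 3 of 25, f = 0.12: bias = +0.06.

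**4. Replacement compared with no replacement.** False superiority is the chance that the two-sided 5% t-test rejects in favour of test. It comes from the noncentral t with noncentrality bias / (0.5 × √(1/n₁ + 1/n₂)); without bias it is 2.5%.

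| Failures in test arm | Bias | Replaced | Excluded, not replaced |
|---|---|---|---|
| 2 of 25 | +0.04 | 25 v 25: 4.6% | 23 v 25: 4.6% |
| 3 of 25 | +0.06 | 25 v 25: 6.1% | 22 v 25: 6.0% |

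For 2 failures the noncentralities are 0.04/(0.5 × √(2/25)) = 0.283 and 0.04/(0.5 × √(1/23 + 1/25)) = 0.277, which give 4.62% and 4.56%. Replacement adds 0.06 percentage points, and 0.17 with 3 failures (6.13% against 5.96%). The rest comes from PP.

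**5. Other patterns.** With the same f and g in both arms, each PP mean moves by f × g and the difference by zero. With failures in control only, the sign reverses.

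**6. Power if places are not refilled.** Exact t at difference 0.4 and SD 0.5: 79.1% at 25 per group, 75.6% at 23 and 73.6% at 22.

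**The case against.** The strongest objection concerns cause: delete section 8.4 and the same subjects are still missing from the PP test, with the same bias. This stands, and the comparison above confirms it. A reader might infer that swapping in new subjects creates the bias, or that a ban on replacement would cure it. The documents support neither: a ban alone would lower power and leave the exclusion in place.

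A reader might also infer that the rule favours the test product. The documents give no failure rate for either arm and do not say that failed grafts have a lower ratio. The endpoint divides new bone by residual graft, so loss of graft material shrinks the denominator, and even the sign of the shift is open.

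A third tempting reading is that a replacement inherits the vacated arm, which would make the next allocation predictable. Section 8.4 speaks only of a new subject with a new number, and section 7.9 routes requests through the sponsor and keeps the list from the centres. The text is silent on inheritance, so this needs a clarification and is not a demonstrated flaw.

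It can also be said that replaced subjects are not erased, since FA and the safety set keep them, and that section 10 promises a detailed analysis plan. Both are true. But section 10.2 already assigns the superiority test to PP, and nothing is assigned to FA.

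**Conclusion.** The concern holds against the choice of PP as the primary set, with section 8.4 as the rule that conceals the resulting losses. Randomised, treated subjects can leave the only superiority test because of events after randomisation, in an open-label trial.

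The size is illustrative. Failures in the test arm only, 2 of 25, with a ratio lower by 0.5, give a bias of +0.04, one tenth of the planned difference of 0.4, and false superiority of about 4.6% against 2.5%. The failure rate, the gap and the placing of all failures in one arm are assumptions. Neither the direction nor the size of any real bias can be read from the documents.

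The point deserves a change before the database is locked, because the remedy is cheap and the primary claim depends on it.

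**What to change.** In section 10.2, run the primary superiority test on all randomised and treated subjects as randomised (the FA set), using every available visit 4 biopsy. Keep PP as a supportive analysis. FA alone does not recover a subject withdrawn before visit 4, who has no ratio, so state a rule for missing biopsies and a sensitivity analysis for them.

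In section 8.4, state that a subject who leaves PP keeps their place in FA; that any additional subject is freshly randomised through section 7.9 and never assigned to a vacated arm; and that the numbers randomised, lost and added are reported by arm.

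The cost is a few sentences in two sections and a missing-data rule in the analysis plan. Including violators may dilute the difference slightly. If fewer than 25 per arm are expected to have a biopsy, the stated 80% should be replaced by the power for that number, as in step 6. If the sponsor wants to keep 80%, the number randomised can be raised openly: at an assumed 10% loss, 25/0.9 = 27.8, or 28 per arm.

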#### 8.5 Missed Visits

In the event a subject misses a visit, the subject should be recalled as soon as possible. At a minimum, the subject should be contacted twice to reschedule. If the subject is not reached by telephone, a certified letter should be sent to the subject. The study monitor should be contacted to discuss options for the subject's continuation in the study. If all attempts to contact the subject have failed, the subject should be considered lost to follow-up and the "Study Termination Form" should be completed.

#### 8.6 Protocol Deviations

Deviations from the procedures established in the protocol are not permitted. If a deviation occurs, the study monitor must be contacted immediately. The deviation must be documented and investigated. A written statement from the investigator on whether the deviation will affect the integrity of the study will be required.

Any deviation from the protocol (including deviations of the visit dates) may jeopardise the study outcome. Non-compliance of the subjects as well as of the investigators may lead to the closure of the respective centre.

### 9 Definitions of Adverse Events and Device Deficiencies (from ISO 14155)

### 9.1 Investigational medical device

Medical device being assessed for safety or performance in a clinical investigation NOTE: This includes medical devices already on the market that are being evaluated for new intended uses, new populations, new materials or design changes.

#### 9.2 Adverse Event (AE)

Any untoward medical occurrence, unintended disease or injury or any untoward clinical signs (including an abnormal laboratory finding) in subjects, users or other persons whether or not related to the investigational medical device.

NOTE 1: This includes events related to the investigational device or the comparator.

NOTE 2: This includes events related to the procedures involved (any procedure in the clinical investigation plan).

NOTE 3: For users or other persons this is restricted to events related to the investigational medical device.

#### 9.3 Expected adverse events

The following adverse events (irrespective of relatedness) can be expected:

- General risks that exist with dental surgical procedures: Bleeding and bruising, pain and swelling after the surgical procedure. Infections in the soft and hard tissue, delayed healing, recession of the gum and/or bone, temporary or permanent nerve damage in the jaw, oro-sinus or oro-nasal fistulas and possible rejection are very rare.
- The following are examples of complications that can generally occur with a surgical procedure using implants and can therefore not be completely ruled out:
  - Slight pain and tenderness the first days after surgery

Version 6.0 Page 24 of 47

- Slight swelling and redness the first days after surgery
- Gingival inflammation (oral hygiene dependent): Oral hygiene instructions are given and oral hygiene procedures performed to prevent gingival inflammation. The occurrence of gingival inflammation will be monitored by means of the modified gingival index and if it occurs the investigator will provide treatment as needed and repeat oral hygiene instructions.
- General risks that exist with a surgical procedure using barrier membranes and can therefore not be completely ruled out: soft tissue dehiscence (tissue damage), haematoma, pain, increased sensitivity and redness due to inflammation.

In regard to wound healing assessments only clinically significant symptoms that are outside the normally accepted range (as judged by the clinician) will be reported as adverse events. This includes, but not restricts to:

- Excessive or progressively increasing pain or discomfort
- Excessive swelling
- Signs of infection (e.g. suppuration)
- Wound / soft tissue breakdown (e.g. soft tissue necrosis, flap dehiscence)
- Any other condition or observation deemed outside of the normal range of healing characteristics

